6.4 Presentation of inferential analyses

For the inferential analyses, the point estimate for the between arm comparison and 95% confidence interval will be reported. Due to the feasibility nature of the study, and the lack of formal power calculation, no p -values will be reported.

6.5 Missing data

The primary analyses for primary and secondary outcomes will be based on complete case data only. For the primary outcomes only, we will use multiple imputation to impute any missing data, if data are missing for more than 5% of participants. Individual item missingness for questionnaire outcomes will be dealt with by using the average of reported items to substitute for missing items if no more than a certain number (to be determined for each questionnaire) of items are missing.

6.6 Adverse events

Data on adverse events will be set out descriptively by trial arm.

7 Audit trail

Date of SAP	SAP version number	Date presented to Trial management group/Trial steering committee	Significant amendments since previous version	Date approved
15 June 2016	1.0	15 June 2016	N/A	15 June 2016
2 December 2019	1.1	5 December 2019	1. Inferential analyses to be adjusted by site (Section 7.3)	5 December 2019
27 January	1.1 (supersedes v1.1. 2/12/2019)	27 January 2020	1. Definition of primary outcome refined and data source for primary outcome confirmed (Section 5.2). 2. Protocol version amended in anticipation of submission (Version 12, 20.01.2020)	27 January 2020
11 March 2020	1.2	12 March 2020	1. Confirmation of use of Protocol Final Version 12, 20.01.2020 (throughout).	12 March 2020

8 References

1. *International Conference on Harmonisation of Technical Requirements for Registration of Pharmaceuticals for Human Use. Statistical Principles for Clinical Trials. Guideline E9.* http://www.ich.org/fileadmin/Public_Web_Site/ICH_Products/Guidelines/Efficacy/E9/Step4/E9_Guideline.pdf (last accessed 25 April 2016)

9 Appendix – example figures and tables

Figure 1 Participant flow diagram

[figure not shown]

Table 3 Participant characteristics at baseline

Participant characteristic	Ketamine + psychotherapy (N=)	Ketamine + psychoeducation (N=)	Placebo + psychotherapy (N=)	Placebo + psychoeducation (N=)
Gender; n (%)				
Male				
Female				
Age; mean (SD); [min, max]				

Table 4 Relapse of alcohol use and percentage of days abstinent at 6-month follow-up: intention to treat population using complete case data.

Outcome	Ketamine (n=)	Placebo (n=)	PT (n=)	PE (n=)	Ketamine + PT (n)	Ketamine + PE (n)	Placebo + PT (n)	Placebo + PE (n)	Ketamine vs placebo RR (95% CI)	Ketamine + PT vs Ketamine + PE RR (95% CI)	Ketamine + PT vs placebo +PE RR (95% CI)
Relapse; n (%) Timeline follow-back											
									Ketamine vs placebo mean difference (95% CI)	Ketamine + PT vs Ketamine + PE mean difference (95% CI)	Ketamine + PT vs placebo +PE mean difference (95% CI)
Percentage days abstinent; mean (SD); median [IQR] Timeline follow-back											

PE: Psychoeducation

PT: Psychotherapy

Table 5 Relapse of alcohol use and percentage of days abstinent at 6-month follow-up: per protocol^a population using complete case data.

Outcome	Ketamine (n=)	Placebo (n=)	PT (n=)	PE (n=)	Ketamine + PT (n)	Ketamine + PE (n)	Placebo + PT (n)	Placebo + PE (n)	Ketamine vs placebo RR (95% CI)	Ketamine + PT vs Ketamine + PE RR (95% CI)	Ketamine + PT vs placebo +PE RR (95% CI)
Relapse; n (%) Timeline follow back											
									Ketamine vs placebo mean difference (95% CI)	Ketamine + PT vs Ketamine + PE mean difference (95% CI)	Ketamine + PT vs placebo +PE mean difference (95% CI)
Percentage days abstinent; mean (SD); median [IQR] Timeline follow back											

^aPer protocol population defined as receiving at least three ketamine infusions. No definition of per protocol for placebo, psychotherapy, or psychoeducation interventions.

PE: Psychoeducation

PT: Psychotherapy

Table 6 Relapse of alcohol use and percentage of days abstinent at 6-month follow-up: intention to treat population using complete case and imputed data.

Outcome	Ketamine (n=)	Placebo (n=)	PT (n=)	PE (n=)	Ketamine + PT (n)	Ketamine + PE (n)	Placebo + PT (n)	Placebo + PE (n)	Ketamine vs placebo RR (95% CI)	Ketamine + PT vs Ketamine + PE RR (95% CI)	Ketamine + PT vs placebo +PE RR (95% CI)
Relapse; n (%) Timeline follow back											
									Ketamine vs placebo mean difference (95% CI)	Ketamine + PT vs Ketamine + PE mean difference (95% CI)	Ketamine + PT vs placebo +PE mean difference (95% CI)
Percentage days abstinent; mean (SD); median [IQR] Timeline follow back											

PE: Psychoeducation

PT: Psychotherapy

Table 7 Secondary outcomes at 3-month follow-up

Outcome	Ketamine (n=)	Placebo (n=)	PT (n=)	PE (n=)	Ketamine + PT (n)	Ketamine + PE (n)	Placebo + PT (n)	Placebo + PE (n)	Ketamine vs placebo mean difference (95% CI)
Number of continuous days abstinent ^{a,b} ; mean (SD), median [IQR]									
Percentage days abstinent ^{a,b} ; mean (SD); median [IQR]									

PE: Psychoeducation

PT: Psychotherapy

^aAbstinent means not using alcohol at all.

^bOutcomes measured using timeline follow-back.

Table 8 Secondary outcomes at 6-month follow-up

Outcome	Ketamine (n=)	Placebo (n=)	PT (n=)	PE (n=)	Ketamine + PT (n)	Ketamine + PE (n)	Placebo + PT (n)	Placebo + PE (n)	Ketamine vs placebo mean difference (95% CI)
Profile of Mood states; mean (SD), n									
Beck Depression Inventory; mean (SD)									
Hamilton Depression Scale; mean (SD), n									
Spielberger Trait Anxiety Inventory; mean (SD), n									
Brief Psychiatric Rating Scale; mean (SD), n									
Psychotomimetic States Inventory; mean (SD), n									
Fagerstrom Test of Nicotine Dependence (FTND); mean (SD), n									
Alcohol Craving Questionnaire (ACQ); mean (SD), n									

Craving (visual analogue scale; mean (SD), n									
Short Form Health Survey 12 (SF-12), physical component scale (PCS); mean (SD), n									
Short Form Health Survey 12 (SF-12), mental component scale (MCS); mean (SD), n									
Episodic memory (Prose Recall); mean (SD), n									
Delay discounting; mean (SD), n									
Response inhibition (Stop Signal Reaction time); mean (SD), n									
Working memory; mean (SD), n									
Hippocampal functioning (Pattern Recognition Test); mean (SD), n									

Adverse effects (visual analogue scale); mean (SD), n									
--	--	--	--	--	--	--	--	--	--

PE: Psychoeducation

PT: Psychotherapy

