### 10.2 Recording adverse events

All adverse events will be recorded in the medical records and CRF only following consent.

If the investigator suspects that the subjects' disease has progressed faster due to the administration of the IMP, then he will record and report

this as an unexpected adverse event. Adverse events that are known to the IMP when used in its licensed indication (listed in Appendix C, or events that are disease related or related to procedures as listed in section 10.3.3) will only be recorded in the medical notes, however serious AEs will be recorded in the CRF and SAE log.

Clinically significant abnormalities in the results of objective tests (e.g. liver function, biochemistry) will also be recorded as adverse events. If the results are not expected as part of disease or IMP, these will also be recorded as unexpected. All adverse events will be recorded with clinical symptoms and accompanied with a simple, brief description of the event, including dates as appropriate. All adverse events will be recorded until 6 months post-treatment. All Serious Adverse Events will be reportable to the Sponsor from IMP administration up to 30 days post last IMP administration.

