### **11.2 Data collection tools and source document identification**

Data to be collected can be found in sections 7.5 and 7.7. Every effort will be made to maximise completeness of data. Trial data will be collected in an Electronic Case Report Form hosted on sealedenvelope.com, prepared using their “Red Pill” service ([www.sealedenvelope.com/redpill](http://www.sealedenvelope.com/redpill)). Source data documents will be defined at site prior to the start of the trial.

Full details of source data and documentation will be identified in a separate source document identification list but in summary will comprise of the following:

- Patient Clinical Record (medical notes)
- Trial specific source data worksheets and trial specific logs

- Laboratory test print outs
- Questionnaires and measurement scales
- Encrypted memory stick containing computer tasks data files and SCRAM-X data

Data to be recorded in the source data first and then transcribed into the CRF:

- Patient demographics; age, date of birth and initials
- Medical history including drug use, alcohol use, smoking
- Physical examination
- Patient eligibility assessment
- Allergies
- Concomitant medication
- Study IMP treatment
- Therapies: Psychoeducation Therapy, Relapse-prevention based CBT
- Clinical Assessment measurements: Vital signs, Blood and urine screen. On infusion visits (visits 2, 4 and 6) continuous monitoring of vital signs will occur through the infusion until the participant has recovered. This monitoring will be recorded on a standard observation chart and will be stored as source data. The eCRF will record 3 sets of readings, one prior to the infusion, another after the infusion terminates, and then finally after the participants recovery.
- Adverse Events (refer to section 10)
- Assessment tools:
  - Pattern Recognition Test
  - Stop Signal Reaction Time
  - Delay Discounting (monetary choice questionnaire)
  - Working Memory (digit span WAIS-IV)
  - Prose Recall
  - SCRAM-X checks
  - BPRS
  - PSI
  - Adverse events VAS
  - Craving VAS
  - Fagerstrom smoking
  - Timeline follow Back
  - Drink diary
  - Reasons for drinking questionnaire
  - Columbia Suicide Severity Rating Scale
  - BDI
  - HAM-D
  - POMS

- STAI
- SF-12
- ACQ-NOW

The following data to be collected in the source documents but will not be collected in the CRF:

- Adverse events that are expected for the IMP and which are not serious and listed in section 10

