## Appendix C: Known Adverse Effects of Ketamine when used in an anaesthetic setting

The following Adverse Events have been reported:

MedDRA System Organ Class	Frequency†	Undesirable Effects
Immune system disorders	Rare	Anaphylactic reaction*
Metabolism and nutrition disorders	Uncommon	Anorexia
Psychiatric disorders	Common	Hallucination, Abnormal dreams, Nightmare, Confusion, Agitation, Abnormal behaviour
	Uncommon	Anxiety
	Rare	Delirium* Flashback*, Dysphoria*, Insomnia, Disorientation*
Nervous system disorders	Common	Nystagmus, Hypertonia, Tonic clonic movements
Eye disorders	Common	Diplopia
	Not Known	Intraocular pressure increased
Cardiac disorders	Common	Blood pressure increased, Heart rate increased
	Uncommon	Bradycardia, Arrhythmia
Vascular disorders	Uncommon	Hypotension
Respiratory, thoracic and mediastinal disorders	Common	Respiratory rate increased
	Uncommon	Respiratory depression, Laryngospasm
	Rare	Obstructive airway disorder*, Apnoea*
Gastrointestinal disorders	Common	Nausea, Vomiting
	Rare	Salivary hypersecretion*
Hepatobiliary disorders	Not known	Liver function test abnormal, Drug-induced liver injury**

Skin and subcutaneous tissue disorders	Common	Erythema, Rash morbilliform
Renal and urinary disorders	Rare	Cystitis*, Haemorrhagic cystitis*
General disorders and administration site conditions	Uncommon	Injection site pain, Injection site rash

† Common ( $\geq 1/100$  to  $< 1/10$ ); Uncommon ( $\geq 1/1,000$  to  $< 1/100$ ); Rare ( $\geq 1/10,000$  to  $< 1/1,000$ ); Not known (frequency cannot be estimated from the available data)

\* AE frequency estimated from post-marketing safety database

\*\* Extended period use (>3 days) or drug abuse

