4.5 Purpose of the analyses

The purposes of the analyses are as follows:

- (i) to provide baseline descriptive data by trial arm;
- (ii) to assess the feasibility of data collection;
- (iii) to assess loss to follow-up at 3 and 6 months;

- (iv) to assess the proportion of missing data at 6 months;
- (v) to provide descriptive outcome data by trial arm (ketamine vs placebo, psychotherapy vs psychoeducation, and all four arms individually) at 6 months;
- (vi) to provide relative risks (with 95% confidence intervals) for relapse of alcohol consumption comparing (a) ketamine vs placebo; (b) ketamine plus psychotherapy vs ketamine plus psychoeducation; (c) ketamine plus psychotherapy vs placebo plus psychoeducation;
- (vii) to provide mean difference (with 95% confidence intervals) for percentage of days abstinent at 6-month follow-up for the same combinations by arm as for (vi); and
- (viii) to descriptively report adverse events.

All inferential analyses are to be regarded as exploratory and viewed with caution due to lack of statistical power and multiple testing. For the primary outcomes, the primary analyses will be performed on an intention to treat (ITT) basis using complete case data only (see Section 6.5 for approaches to missing primary outcome data). As a sensitivity analysis, the inferential analyses for the primary outcomes only (vi and vii above) will be performed using only those participants deemed to have completed their allocated interventions to a specified degree (per protocol analysis). For the participants who receive ketamine, a per protocol treatment will be defined as receiving three or more infusions. No specification of a minimum treatment has been defined for psychotherapy/psychoeducation. Hence, all participants who receive placebo drug therapy will be considered as having been treated per protocol. For the secondary outcomes, only an ITT analysis using complete case data will be performed. All analyses will be performed by a statistician who is blinded to treatment allocation. All analyses will be performed using Stata v14.

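### The SAP summarises adverse events by arm but not the infusion-day vital signs held in the eCRF, and one reading of Protocol 10.2 keeps non-serious blood-pressure and heart-rate events out of that summary

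*SAP*

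**What the plan says.** SAP 5.1 repeats the protocol's second primary objective, the safety and tolerability of ketamine. The eight analysis purposes in SAP 4.5 contain one item on harms, the eighth: "to descriptively report adverse events". SAP 6.6 is a single sentence: "Data on adverse events will be set out descriptively by trial arm". The remaining physical-safety measure is the adverse-effects VAS, which SAP Table 2 and Table 8 place at 6 months.

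Protocol 10.2 says what reaches the adverse-event data, in three statements:

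- The general rule: "All adverse events will be recorded in the medical records and CRF only following consent".
- The specific rule for events known for the drug and listed in Appendix C, and for the disease- or procedure-related events of 10.3.3. These "will only be recorded in the medical notes, however serious AEs will be recorded in the CRF and SAE log".
- The rule on tests: "Clinically significant abnormalities in the results of objective tests (e.g. liver function, biochemistry) will also be recorded as adverse events".

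Protocol 11.2 lists what is kept in source documents but not in the CRF: "Adverse events that are expected for the IMP and which are not serious and listed in section 10". Appendix C includes "Blood pressure increased, Heart rate increased" (Common) and "Bradycardia, Arrhythmia" (Uncommon), with hypotension also Uncommon.

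Protocol 7.5, 7.7 and 11.2 put three sets of vital signs into the eCRF at each infusion visit (2, 4 and 6): before the infusion, after it ends, and after recovery. Protocol 7.9.1 and note b to Appendix B include blood pressure, resting pulse and pulse oximetry among the vital signs and give safety monitoring as the purpose.

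**The concern.** Raised blood pressure, respiratory rate and heart rate is the first risk that Protocol 2.5 lists for the drug. The frequencies there come from anaesthetic use. The trial's 0.8 mg/kg over 40 minutes is slower and lower than an anaesthetic dose, but above the 0.5 mg/kg for which section 2.4 cites tolerability in recently detoxified patients. The trial's own comparison with placebo is therefore useful evidence on a primary objective.

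If sites follow the specific sentence in 10.2, the by-arm adverse-event table will leave out non-serious rises in blood pressure and heart rate, bradycardia, hypotension and arrhythmia. A low or zero count would then partly reflect the recording rule, and could be read as reassurance when a larger trial is considered. The eCRF readings could show the blood-pressure and pulse effects directly, but no analysis of them is planned.

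**Working it through.** The plan states no figure on this point, so there is none to reproduce. The check is textual, with simple counts for scale.

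**1. Are the vital signs used anywhere in the SAP?** They do not appear in the purposes (4.5), endpoints (5.2), derived variables (5.3), Table 2, section 6.6 or example Tables 3 to 8. SAP 4.5(i) and Protocol 13.3.1 promise baseline summaries. These could cover pre-infusion values at visit 2, but not the change over an infusion.

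**2. Can the 6-month VAS stand in?** From the visit windows in Protocol 7.7:

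- Visit 6 (third infusion) is 4 + 4 = 8 to 21 + 21 = 42 days after visit 2.
- Visit 10 is 23 × 7 = 161 to 25 × 7 = 175 days after visit 2.
- The gap is 161 − 42 = 119 to 175 − 8 = 167 days.

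The VAS items given as examples in 7.5 (nausea, intoxication, anxiety, memory) do not measure blood pressure or pulse in any case.

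**3. Do non-serious blood-pressure events reach the CRF?** The general sentence in 10.2 says yes. The specific sentence says no, because these events are in Appendix C. A specific exception normally qualifies a general rule. The tests sentence could cover a clinically significant reading, but its examples are laboratory tests and it does not expressly lift the exception. Section 11.2 refers to events listed in section 10. Appendix C lies outside section 10 and is reached only through 10.2, so 11.2 is not independent support. The notes-only reading is the more natural one, but not certain.

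**4. How many events could be affected?** With 24 per cell, 48 participants are allocated to ketamine. Assume that Appendix C's Common band (1% to under 10%) applies per participant at the trial dose:

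| Rate | Expected of 48 | P(none) = (1 − rate)^48 |
|---|---|---|
| 1% | 0.48 | 62% |
| 5% | 2.4 | 9% |
| 10% | 4.8 | 0.6% |

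Under the notes-only reading, none of the non-serious cases reach the CRF; under the general reading, all do. If the table showed 0 of 48, the exact two-sided 95% upper limit would be 1 − 0.025^(1/48) = 7.4%. That limit would be unsupported if the zero came from the recording rule.

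**5. What data are available?** At visit 2, 96 × 3 = 288 sets if everyone is dosed; over three infusions, up to 96 × 3 × 3 = 864 sets, of which 48 × 9 = 432 are from ketamine participants.

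**6. How precise would an optional between-arm difference be?** For the change in systolic pressure at visit 2, with arm and site in the model, the 95% half-width is t × SD × √(2/n per arm). The documents give no SD; 10 to 15 mmHg is an assumption.

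- 48 vs 48: 1.986 × √(2/48) = 0.405 SD, or 4.1 to 6.1 mmHg.
- 24 vs 24: 2.014 × √(2/24) = 0.581 SD, or 5.8 to 8.7 mmHg.

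**The case against.** The strongest reply is that the harm depends on a disputed reading. Section 10.2 opens by sending every event to the CRF, 11.2 lists adverse events among the data transcribed there, and the list printed in 10.3.3 does not name blood pressure, pulse or rhythm. If sites follow the general rule, the by-arm table is not biased in this way. This stands as a limit on certainty. It does not remove the absence of any planned vital-signs summary, which holds on either reading.

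Second, vital signs are a monitoring variable, not a listed outcome. The SAP follows the protocol, its tables are labelled as examples (with no adverse-event table either), and nothing forbids an extra table. All true. But the purposes in SAP 4.5 are not examples, and they omit vital signs too. With safety a primary objective, the commitment is better made before results are seen.

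Third, the false-reassurance argument is modest. An upper limit of 7.4% is compatible with most of the Common band, a zero is likely anyway at a true rate of 1%, and these effects are already known. This also stands.

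A reader might go further and infer that haemodynamic safety data are lost, or that participants are unprotected. The documents do not support either. The readings are in the eCRF, the continuous observation chart is kept as source data, and vital signs are watched throughout each infusion until recovery.

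**Conclusion.** The point holds as a gap in planned reporting, and is worth correcting before analysis. The SAP has no summary of infusion-day vital signs, although safety is a primary objective and the readings are held for both arms. On the more specific, but not certain, reading of Protocol 10.2, the by-arm adverse-event table would also understate non-serious Appendix C effects. For each Common event, that is about 0.5 to 4.8 of 48 ketamine participants if anaesthetic-use rates applied. The trial dose is lower and slower, so the true number may differ.

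It would be too strong to say that the protocol definitely bars these events from the CRF, or that 11.2 confirms this independently: the general sentence in 10.2 points the other way, and 11.2 reaches Appendix C only through 10.2. The primary outcome estimates and the interim attrition rule are unaffected.

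**What to change.** Add to SAP 6.6 one descriptive table by drug arm, for everyone given at least one infusion. It should cover systolic pressure, diastolic pressure, pulse and oxygen saturation before infusion, after infusion and at recovery, with the pre- to post-infusion change, at visits 2, 4 and 6 (n, mean, SD and range). That is 4 × 3 × 3 = 36 rows plus 4 × 3 = 12 change rows. State that this population is an exception to SAP 4.7, which drops participants found ineligible after randomisation from all analyses.

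A between-arm interval is optional. If one is wanted, use the change in systolic pressure at visit 2, adjusted for site as in SAP 6.3 and without a p-value. Visit 2 is preferable because Protocol 9.11 withdraws people with intolerable effects from later infusions.

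Footnote the adverse-event table to say whether non-serious Appendix C events were collected in the CRF.

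Produce the vital-signs table only after the blinded primary analyses are finished. SAP 4.4 and 4.5 keep the statistician blinded, and blood pressure by coded arm could reveal which code is ketamine.

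The cost is SAP wording and a little more analysis work, with no new data collection and no protocol change. Two limits remain: three readings per infusion may miss a peak during the infusion, and non-serious rhythm events are not recovered by these readings.
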